11.3. Appendix 3: Treatment States and Phases

Study treatment start date/time and/or stop date/time are determined by the infusion of IP administered. For retreated subjects, start date/time and stop date/time for both initial treatment and retreatment will be derived.

11.3.1. Treatment Phases

Assessments and events will be classified according to the time of occurrence relative to study treatment, unless otherwise specified.

Non-retreated subjects

Treatment Phase	Definition
Pre-treatment	Date/Time < Initial Study Treatment Start Date/Time
On-treatment	Initial Study Treatment Start Date Time ≤ Date Time ≤ Initial Study Treatment Stop Date Time + 12 hours or Retreated Study Treatment Start Date Time ≤ Date Time ≤ Retreated Study Treatment Stop Date Time + 12 hours
Post-treatment	Study Treatment Stop Date/Time + 12 hours < Date Time < Retreated Study Treatment Start Date Time or Date/Time > Retreated Study Treatment Stop Date/Time + 12 hours

Retreated subjects

Treatment Phase	Definition
Pre-treatment	Date/Time < Initial Study Treatment Start Date/Time
On-treatment	Initial Study Treatment Start Date Time ≤ Date Time ≤ Initial Study Treatment Stop Date Time + 12 hours or Retreated Study Treatment Start Date Time ≤ Date Time ≤ Retreated Study Treatment Stop Date Time + 12 hours
Post-treatment	Study Treatment Stop Date/Time + 12 hours < Date Time < Retreated Study Treatment Start Date Time or Date/Time > Retreated Study Treatment Stop Date/Time + 12 hours

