8.2.6.2. Fetal Heart Rate

Summaries for fetal heart rate will be performed using the Maternal Safety Population.

A table will summarize categorical fetal heart rate results by treatment group during treatment phase and post-treatment phase. Categories to be presented are Category I, II and III based on ACOG guidelines [ACOG, 2009].

All fetal heart rate data by subject will be presented in a listing.

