11.3.3. Treatment States for AE Data

Non-retreated subjects

Treatment State	Definition
AE = Pre-treatment	AE Start Date < Study Treatment Start Date
AE = On-treatment	If AE onset date is on or after the treatment start date and on or before the treatment stop date. Study Treatment Start Date \leq AE Start Date \leq Study Treatment Stop Date + 1
AE = Post-treatment	If AE onset date is after the treatment stop date. AE Start Date > Study Treatment Stop Date + 1
AE Onset Time Since 1 st Dose (Days)	If Study Treatment Start Date > AE Onset Date : = AE Onset Date – Study Treatment Start Date If Treatment Start Date \leq AE Onset Date : = AE Onset Date – Study Treatment Start Date + 1 Missing otherwise
AE Duration (Days)	AE Resolution Date – AE Onset Date + 1
AE = Drug-related	If relationship is marked 'YES' on [Inform/CRF OR value is missing.

NOTES:

- If the study treatment stop date is missing then the AE will be considered to be On-Treatment if there are no post-infusion assessments and delivery.

Retreated subjects

Treatment State	Definition
AE = Pre-treatment	AE Start Date < Initial Study Treatment Start Date
AE = On-treatment	If AE onset date is on or after the treatment start date and on or before the treatment stop date. Initial Study Treatment Start Date \leq AE Start Date \leq Initial Study Treatment Stop Date + 1 or Retreated Study Treatment Start Date \leq AE Start Date \leq Retreated Study Treatment Stop Date + 1
AE = Post-treatment	If AE onset date is after the treatment stop date. Initial Study Treatment Stop Date + 1 < AE Start Date < Retreated Study Treatment Start Date or AE Start Date > Retreated Study Treatment Stop Date + 1
AE Onset Time Since 1 st Dose (Days)	If Initial Study Treatment Start Date > AE Onset Date : = AE Onset Date – Initial Study Treatment Start Date If Initial Study Treatment Start Date \leq AE Onset Date : = AE Onset Date – Initial Study Treatment Start Date + 1 Missing otherwise

Treatment State	Definition
AE Duration (Days)	AE Resolution Date – AE Onset Date + 1
AE = Drug-related	If relationship is marked 'YES' on [lInform/CRF OR value is missing.

NOTES:

- If the study treatment stop date is missing then the AE will be considered to be On-Treatment if there are no post-infusion assessments and delivery.

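### SAP 11.3.1 gives women treated once a post-treatment rule that needs retreatment dates, and SAP 11.3.3 states two different end points for on-treatment adverse events

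*SAP*

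**What the plan says.** SAP Appendix 3 (11.3) classifies records by their time relative to study treatment. It says of retreatment dates: "For retreated subjects, start date/time and stop date/time for both initial treatment and retreatment will be derived". No such dates are derived for women treated once.

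SAP 11.3.1 then gives two tables, one for non-retreated and one for retreated subjects, with identical contents. In both, a record is post-treatment if either of two conditions holds:

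- "Study Treatment Stop Date/Time + 12 hours < Date Time < Retreated Study Treatment Start Date Time"
- "Date/Time > Retreated Study Treatment Stop Date/Time + 12 hours"

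SAP 8.2.6.2 plans a display by phase: "A table will summarize categorical fetal heart rate results by treatment group during treatment phase and post-treatment phase". This is Table 3.424, which remains in the reduced list of outputs in SAP 11.11.

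SAP 11.3.3 has its own rules for adverse events, by date rather than by time. Each row pairs a sentence with a formula. For women not retreated:

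- On-treatment, in words: "If AE onset date is on or after the treatment start date and on or before the treatment stop date". Formula: "Study Treatment Start Date \leq AE Start Date \leq Study Treatment Stop Date + 1".
- Post-treatment, in words: "If AE onset date is after the treatment stop date". Formula: "AE Start Date > Study Treatment Stop Date + 1".

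The retreated-subject rows pair words and formulas in the same way.

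**The concern.** These are two separate drafting faults in one appendix.

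The first is a rule whose input does not exist for the women it covers. A woman in the non-retreated table has, by definition, no retreatment start or stop, yet both routes into her post-treatment phase compare against one. A programmer who follows the text cannot place her later records correctly. Fetal heart rate is collected after the infusion, at the face-to-face visit and, if available, just before delivery. Category II or III tracings are a fetal adverse event of special interest.

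The second is a rule that contradicts itself. Two programmers could count an adverse event that begins the day after the infusion stops in different states, and each could point to the SAP. The most-common on-treatment event summaries (SAP 8.2.3.3, for example Table 3.41) depend on this boundary. So do the maternal AE and SAE summaries by phase described in SAP 8.2.3.1 and 8.2.3.4.

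**Working it through.** The plan gives no figure to reproduce, so the check applies the written rules literally.

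**Phase rule, woman treated once.** Illustrative assumption: a 48-hour infusion, so start = 0 h, stop = 48 h and stop + 12 = 60 h, with both retreatment times missing. The SAP does not say how a missing date compares with an observed one, so both possibilities are shown.

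| Hours from start | Comparison with missing is false | Missing sorts below every value | Rule without retreatment dates |
|---|---|---|---|
| -2 | pre | pre and post | pre |
| 10 | on | on and post | on |
| 54 | on | on and post | on |
| 60 | on | on and post | on |
| 61 | none | post | post |
| 100 | none | post | post |
| 500 | none | post | post |

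The first post-treatment condition (60 < time < missing) is never true under either convention. The second (time > missing + 12) is never true under one and always true under the other. So either nothing is post-treatment, or everything is. The on-treatment row also carries a retreatment condition, but it does no harm: that condition is never met, and the row works through its first condition (0 ≤ time ≤ 60). In the last column post-treatment is simply time > 60, and every tested time falls in exactly one phase.

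**Adverse-event rule.** Compare words and formula by onset date:

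| Onset date | By the words | By the formula |
|---|---|---|
| Stop date | on | on |
| Stop date + 1 | post | on |
| Stop date + 2 | post | post |

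Only the calendar day after the stop date is in dispute.

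**Comparison with the 12-hour window of 11.3.1.** If the infusion stops at clock hour h, the words leave 24 - h hours of on-treatment time after the stop, and the formula leaves 48 - h.

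| Stop at | Words | Formula | 11.3.1 |
|---|---|---|---|
| 06:00 | 18 h | 42 h | 12 h |
| 14:00 | 10 h | 34 h | 12 h |
| 18:00 | 6 h | 30 h | 12 h |

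The words give less than 12 hours whenever the infusion stops after noon. The formula always gives more than 24 hours, so it always contains the 12-hour window.

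**How much one event can matter.** SAP 8.2.3.3 lists events with incidence above 2%, and SAP 2.3 gives 97 women randomized 1:1. Assume about 48 dosed per arm, since the SAP does not give the number dosed. One woman is then 1/48 = 2.1%. If the cut-off applies per arm, one reclassified event can move a term into or out of the table; in an arm of 50 or more it would take two women (1/50 = 2.0%, not above the cut-off). If it applies to both arms together, two women are needed: 1/97 = 1.03%, 2/97 = 2.06%.

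**The case against.** The best defence is that faulty text need not produce faulty output. SAP section 3 leaves variable derivations to an ADaM specification outside these documents. A program that assigns pre, then on, and calls the remainder post would classify women treated once correctly. SAP 8.2.6.2 does not cite 11.3.1, and visit labels would separate most fetal heart rate records: those during the infusion are taken with maternal vital signs, and the face-to-face visit falls 3 to 14 days after the treatment phase. The main exception is a record near the boundary, such as a delivery soon after the infusion.

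On adverse events, 11.3.1 applies only where nothing else is specified. The maternal AE and SAE phase summaries are sent to 11.3.3, whose non-retreated rule needs no retreatment date. The general AE tables count any event starting on or after first treatment (SAP 8.2.3), so the boundary does not move them. No maternal AE or SAE table title in SAP 11.11.5 names a split by phase.

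All of this stands as a limit on the consequences. It does not make the printed rules usable. An else-post program would depart from the text to repair it, and the self-contradiction in 11.3.3 remains for the on-treatment summaries and for any phase split within Tables 3.11 and 3.51.

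**Conclusion.** Both faults are real and small. The non-retreated rule in 11.3.1 appears to be a copy of the retreated rule and fails under either treatment of missing dates. The AE rows in 11.3.3 disagree with their own formulas by one calendar day, in both the on-treatment and post-treatment rows, for retreated and non-retreated women alike.

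The first covers every woman treated once, but that counts people under the rule, not records misclassified. It reaches output only if a display by phase outside the AE data, chiefly Table 3.424, is built from 11.3.1. The second reaches only events that start on the day after the stop date. The documents give no count of affected records or events for either. Safety data have no formal hypothesis tests, and no efficacy result, power or error rate changes.

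A reader might infer four stronger things that the documents do not support:

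- That every record will be counted as post-treatment because SAS ranks missing values lowest. The SAP names SAS but does not state this behaviour, and the point does not need it.
- That the fetal heart rate table will have no valid post-treatment data for women treated once. That depends on programming not shown here.
- That a full day of the two-day infusion changes category. The disputed day is the one after the infusion stops.
- That the formula is known to be the intended AE rule. Nothing in the SAP settles this.

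**What to change.** In the non-retreated table of SAP 11.3.1, remove all retreatment dates:

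- on-treatment: start ≤ time ≤ stop + 12 hours
- post-treatment: time > stop + 12 hours

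In SAP 8.2.6.2, state whether the fetal heart rate table uses these definitions.

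In SAP 11.3.3, adopt one end point in both the words and the formulas of the on-treatment and post-treatment rows, for non-retreated and retreated women. Stop date + 1 is the better-supported choice because, at date level, it always contains the 12-hour window. The sponsor should confirm it and add a sentence on how it relates to that window.

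The cost is a few lines in two SAP tables, plus a check that the ADaM specification matches. It should be done before database freeze and unblinding, when the SAP synopsis requires decisions on the final analyses to be settled.

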11.3.2. Treatment States

Assessments and events will be classified according to time of occurrence relative to the start and/or stop date/time of the study treatment.

11.3.3. Treatment States for AE Data

Non-retreated subjects

Treatment State	Definition
AE = Pre-treatment	AE Start Date < Study Treatment Start Date
AE = On-treatment	If AE onset date is on or after the treatment start date and on or before the treatment stop date. Study Treatment Start Date \leq AE Start Date \leq Study Treatment Stop Date + 1
AE = Post-treatment	If AE onset date is after the treatment stop date. AE Start Date > Study Treatment Stop Date + 1
AE Onset Time Since 1 st Dose (Days)	If Study Treatment Start Date > AE Onset Date : = AE Onset Date – Study Treatment Start Date If Treatment Start Date \leq AE Onset Date : = AE Onset Date – Study Treatment Start Date + 1 Missing otherwise
AE Duration (Days)	AE Resolution Date – AE Onset Date + 1
AE = Drug-related	If relationship is marked 'YES' on [Inform/CRF OR value is missing.

NOTES:

- If the study treatment stop date is missing then the AE will be considered to be On-Treatment if there are no post-infusion assessments and delivery.

Retreated subjects

Treatment State	Definition
AE = Pre-treatment	AE Start Date < Initial Study Treatment Start Date
AE = On-treatment	If AE onset date is on or after the treatment start date and on or before the treatment stop date. Initial Study Treatment Start Date \leq AE Start Date \leq Initial Study Treatment Stop Date + 1 or Retreated Study Treatment Start Date \leq AE Start Date \leq Retreated Study Treatment Stop Date + 1
AE = Post-treatment	If AE onset date is after the treatment stop date. Initial Study Treatment Stop Date + 1 < AE Start Date < Retreated Study Treatment Start Date or AE Start Date > Retreated Study Treatment Stop Date + 1
AE Onset Time Since 1 st Dose (Days)	If Initial Study Treatment Start Date > AE Onset Date : = AE Onset Date – Initial Study Treatment Start Date If Initial Study Treatment Start Date \leq AE Onset Date : = AE Onset Date – Initial Study Treatment Start Date + 1 Missing otherwise

Treatment State	Definition
AE Duration (Days)	AE Resolution Date – AE Onset Date + 1
AE = Drug-related	If relationship is marked 'YES' on [lInform/CRF OR value is missing.

NOTES:

- If the study treatment stop date is missing then the AE will be considered to be On-Treatment if there are no post-infusion assessments and delivery.

11.4. Appendix 4: Data Display Standards & Handling Conventions

11.4.1. Study Treatment & Sub-group Display Descriptors

Study Treatment Descriptions		
Code	Description	Order of Table Presentation
1	Retosiban	2
2	Atosiban	1

11.4.2. Baseline Definition & Derivations

11.4.2.1. Baseline Definitions

For all endpoints (expect as noted) baseline value will be the latest pre-dose assessment. For the retreated subjects, a baseline will be the latest pre-dose assessment of the initial treatment.

Parameter	Study Assessments Considered As Baseline		Baseline Used in Data Display
	Screening	Day 1 (Pre Dose)	
Safety			
Vital Signs	X	X	Last value to prior to start of IP
Laboratory	X		Screening

11.4.2.2. Derivations and Handling of Missing Baseline Data

Definition	Reporting Details
Change from Baseline	= Post-Dose Visit Value – Baseline

NOTE :

- Unless otherwise specified, the baseline definitions specified in 11.4.2.1 Baseline Definitions will be used for derivations for endpoints / parameters and indicated on summaries and listings.
- Unless otherwise stated, if baseline data are missing no derivation will be performed and baseline value will be set to missing.
- The baseline definition will be footnoted on all change from baseline displays.

The baseline is defined as last assessment prior of start of IP administration. The value will be missing if the baseline data are missing. For lab parameters, last assessment prior to IP will be used as baseline if there are multiple assessments at screening or day 1.

11.4.3. Reporting Process & Standards

Reporting Process
Software

 The currently supported versions of SAS software will be used to perform all data analyses, generate tables, figures, and listings.
Reporting Area
Analysis Datasets

 Analysis datasets will be created according to ADaM implementation guide version xx. RTF files will be generated. All datasets are CDISC compliance.
Reporting Standards
General

 The current GSK Integrated Data Standards Library (IDSL) will be applied for reporting, unless otherwise stated: 
 4.03 to 4.23: General Principles 5.01 to 5.08: Principles Related to Data Listings 6.01 to 6.11: Principles Related to Summary Tables 7.01 to 7.13: Principles Related to Graphics
Formats

 For study population and efficacy analyses, all data will be reported according to the planned treatment the subject was randomized unless otherwise stated. For safety analyses, all data will be reported according to the actual treatment the subject received unless otherwise stated. GSK IDSL Statistical Principles (5.03 & 6.06.3) for decimal places (DP's) will be adopted for reporting of data based on the raw data collected. Numeric data will be reported at the precision collected on the eCRF. The reported precision from non eCRF sources will follow the IDSL statistical principles but may be adjusted to a clinically interpretable number of DP's.

Planned and Actual Time	

• Reporting for tables, figures and formal statistical analyses :
• Planned time relative to dosing will be used in figures, summaries, statistical analyses and calculation of any derived parameters, unless otherwise stated.• The impact of any major deviation from the planned assessment times and/or scheduled visit days on the analyses and interpretation of the results will be assessed as appropriate.• Reporting for Data Listings:
• Planned and actual time relative to study drug dosing will be shown in listings (Refer to IDSL Statistical Principle 5.05.1).• Unscheduled or unplanned readings will be presented within the subject's listings.• Visits outside the protocol defined time-windows (i.e. recorded as protocol deviations) will be included in listings but omitted from figures, summaries and statistical analyses.	
Unscheduled Visits	

• Unscheduled visits will not be included in by-visit summary tables or figures except 'any visit post-baseline category', unless otherwise stated.• All unscheduled visits will be listed.	
Descriptive Summary Statistics	
Continuous Data	Refer to IDSL Statistical Principle 6.06.1
Categorical Data	N, n, frequency, %
Graphical Displays	

• Refer to IDSL Statistical Principles 7.01 to 7.13.	

11.5. Appendix 5: Derived and Transformed Data

11.5.1. General

Multiple Measurements at One Time Point

- Mean of the measurements will be calculated and used in any derivation of summary statistics but if listed, all data will be presented.
- For laboratory assessment and vital signs' descriptive summary statistics and other endpoints, if there are multiple assessments within a same scheduled visit, the last assessment within the visit will be used.
- For laboratory assessment and vital signs with potential clinical importance, if there are two values within a time window, the worst value (i.e. the most extreme value from the normal range) will be used.
- Subjects having both High and Low values for Normal Ranges at any post-baseline visits for safety parameters will be counted in both the High and Low categories of "Any visit post-baseline" row of related summary tables. Unscheduled visit will be included. This will also be applicable to relevant Potential Clinical Importance summary tables.

Study Day

- Calculated as the number of days from the first study treatment date :
 - [1] Ref Date = Missing → Study Day = Missing (none displayed)
 - [2] Ref Date < First Study Treatment Date → Study Day = Ref Date – First Study Treatment Date
 - [3] Ref Date ≥ First Study Treatment Date → Study Day = Ref Date – (First Study Treatment Date) + 1

11.5.2. Study Population

Demographics

Age for Mother

- GSK standard IDSL algorithms will be used for calculating age where birth date will be imputed as follows:
 - [1] Date of birth of any subject will have this imputed as '30th June'.
 - [2] If a subject is recorded as an adolescence in CRF and imputed date of birth in [1] is > 18 years old, the last possible date to be 18 years old will be assigned. For example, an adolescence's randomization date is 30Jun2016 and birth year is 1998. Imputed date of birth in [1] is 30Jun1998 and age is 19 years old. Then 29Jun1998 will be used as birth date to keep the subject in adolescence category.
- Birth date will be presented in listings as 'YYYY'.

Body Mass Index (BMI)

- Calculated as Weight (kg) / [Height (m)]²

Extent of Exposure

- Number of hours of exposure to study drug will be calculated using dates from the trial medication form. The duration of exposure in days will be based on the formula:

Duration of Exposure in Hours = (Treatment Stop Date/Time (in minutes) – Start Date/Time (in minutes))/60

- If there are any treatment interruptions during the study, then the exposure data will be adjusted accordingly.

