6.3. Demographic and Baseline Characteristics

For mothers, continuous variables, such as age (years), weight (kg), height (cm), BMI (kg/m²), gestational age at randomization (weeks/day), contraction frequency, cervical

dilation (cm), cervical length (mm), percentage of women who failed PTL criteria (inclusion criteria #4), fFN (continuous) and other baseline characteristics as needed will be summarized using descriptive statistics by treatment group. Since only year of birth is collected and the month and day of birth are not collected, a mother's age will be calculated using below algorithm.

- The day and month is imputed as '30th June'.
- The age of mother is calculated as the difference of the date of the first study treatment and the date of birth divided by 365.25. For example, if the date of the randomization was at 00:00 am on 20 March 2015 and date of birth was 1987, the age is 27.
- If no inclusion deviation in age requirement, the age is between 12 and 45 year old based on study entry criteria.
- The mother is recorded as an adolescent in CRF if she is adolescent (12 to < 18 years of age), so age will be adjusted. For example, the calculated age is 18.2 but a subject is marked as an adolescent in CRF, a subject's age is to 18.

GA at randomization in weeks/days will be obtained from CRF and will be converted into numeric value as covariate in the statistical analysis of primary and secondary endpoint. Please refer to Appendix 11.6.2 for missing GA at randomization.

The following categorical variables will be summarized by reporting the number and percentage of subjects in each category by treatment group:

- Race
- Ethnicity
- GA at randomization (4 GA strata: $24^{0/7}$ to $25^{6/7}$, $26^{0/7}$ to $27^{6/7}$, $28^{0/7}$ to $30^{6/7}$ and $31^{0/7}$ to $33^{6/7}$)
- Established progesterone use
- Region
- Prior tocolytic use in current episode (Beta-mimetics, Magnesium Sulfate, Calcium channel Blockers, NSAIDs, and Oxytocin receptor antagonists)
- Adolescent (between 12-<18 years) and adult (≥ 18 years) patients.
- fFN (positive or negative)

For fetus, continuous variables, such as estimated weight (g) and AFI results (cm) measured using the 4-quadrant method will be summarized.

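### The age adjustment for CRF-flagged adolescents stops at 18, which the SAP itself classes as adult, and its worked example is arithmetically wrong

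*SAP*

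**What the plan says.** SAP 6.3 (Demographic and Baseline Characteristics) and SAP 11.5.2 (Age for Mother) both describe how maternal age is derived when only the birth year is known.

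- Starting point, 11.5.2: "Date of birth of any subject will have this imputed as '30th June"; 6.3 does the same.
- Age formula, 6.3: "The age of mother is calculated as the difference of the date of the first study treatment and the date of birth divided by 365.25".
- Categories to be summarized, 6.3: "Adolescent (between 12-<18 years) and adult", with adult starting at 18. The same section describes the CRF adolescent flag as covering 12 to under 18.
- Adjustment in 11.5.2, which applies to a flagged adolescent: "imputed date of birth in [1] is > 18 years old, the last possible date to be 18 years old will be assigned".
- Worked example in 11.5.2: a flagged girl with birth year 1998 is randomized on 30Jun2016. The SAP puts her at 19 under the 30 June imputation and resolves the case this way: "Then 29Jun1998 will be used as birth date to keep the subject in adolescence category".
- Adjustment in 6.3: its illustration is a mother for whom "the calculated age is 18.2 but a subject is marked as an adolescent in CRF". That section resets her to 18.

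**The concern.** An adjustment meant to hold a flagged girl in the adolescent category has to end below 18. Both statements of it end at 18, the first age in the adult category. The example also replaces a birth date with an earlier one, which can only raise the age.

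At stake is the agreement between the reported age, the reported category and the CRF flag for minors. The protocol (3.2.2) discusses this group separately and notes that atosiban's safety and efficacy are not established under 18. A programmer who follows the example literally would build the error into the dataset.

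**Working it through.** **Inputs.** From SAP 6.3: the age formula (reference date minus birth date, divided by 365.25) and the cut at 18. From SAP 11.5.2: the 30 June imputation, the trigger (above 18), the target (the last date on which she would be 18), and the example dates. The 11.5.2 example uses the randomization date as reference, whereas the 6.3 formula uses first treatment. They are taken as the same day here.

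**Check of the formula on the SAP's own case.** SAP 6.3 gives birth year 1987, randomization on 20 March 2015, age 27. From 30Jun1987 to 20Mar2015 is 10,125 days; 10,125 / 365.25 = 27.72, truncated to 27. The formula reproduces.

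**The 11.5.2 example, reference date 30Jun2016.**

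| Birth date | Days | Days / 365.25 | Completed years | SAP 6.3 category |
|---|---|---|---|---|
| 30Jun1998 (imputed) | 6575 | 18.0014 | 18 | adult |
| 29Jun1998 (SAP's replacement) | 6576 | 18.0041 | 18 | adult |
| 01Jul1998 | 6574 | 17.9986 | 17 | adolescent |

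The stated age of 19 does not reproduce under either convention, and the replacement date adds a day to her age. The example also disagrees with the rule it illustrates: the latest birth date at which she is already 18 on 30Jun2016 is 30Jun1998 itself, so the rule text would leave the date where it was.

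**Could the randomization year be a misprint?** With 30Jun2017, 30Jun1998 does give 19 (19.0007), but 29Jun1998 still gives 19 (19.0034). A misprint does not rescue the example.

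**The rule text away from the example.** Take the 18.2-year case of SAP 6.3: birth year 1998, reference date 11Sep2016.

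- 30Jun1998: 6648 days, 18.2012.
- 11Sep1998, the last date on which she is 18: 6575 days, 18.0014, adult.
- 12Sep1998: 6574 days, 17.9986, adolescent.

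Here the rule moves the date later, in the right direction, but stops one day short. The flat reset to 18 in 6.3 ends in the same place.

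**The trigger.** In completed years the example subject is exactly 18, so a test for above 18 does not fire and her age stays at 18. It fires only on the decimal age (18.0014).

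**Who is affected.** Only flagged adolescents whose 30 June imputation already gives 18 or more. A girl born in 1998 and randomized on 01Mar2016 has imputed age 6454 / 365.25 = 17.67 and never meets the trigger. The affected group is therefore those dosed on or after about 30 June of the year they turn 18, with the birthday still to come.

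**The case against.** Four stronger conclusions are tempting, and the documents do not support them.

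1. *The rule always moves the birth date the wrong way.* Only the worked example does. For reference dates after 30 June, the rule text moves the date later. Its fault is the target, not the direction.
2. *Minors are certainly tabulated as adults and undercounted.* Neither section says whether the adolescent/adult row is computed from numeric age or read from the CRF flag. SAP 6.3 treats the flag as authoritative and adjusts the age to fit it. If the row uses the flag, nobody is misclassified. What remains is an age of 18 reported for someone labelled adolescent.
3. *Every girl turning 18 in the randomization year is affected.* Those dosed before 30 June are not. Nor does 11.5.2 fail in every remaining case: dividing by 365.25, the exact 18-year date gives 6574 days (17.9986) for reference dates in the second half of 2014 or 2015, and 6575 days (18.0014) in the second half of 2016 or 2017. That accident of leap years does not help in completed years, and it does not rescue the flat reset to 18 in 6.3.
4. *Efficacy or safety conclusions are at risk.* Maternal age is in neither the primary model (SAP 7.1.2) nor the key secondary models (8.1.2), and the SAP's named subgroups (5.1) do not use it. Protocol 8.3.5.2 lists maternal age as an optional safety subgroup, but the SAP does not carry it forward. Birth date is listed only as a year, so the one-day shift would not be visible in listings.

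The trial stopped at 97 patients, Sweden took adults only, and the documents do not show that any flagged adolescent fell in the affected window. All of this limits the consequence. None of it makes the rule or the example correct.

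**Conclusion.** The point holds as a minor error in an operative derivation. SAP 11.5.2 and 6.3 lower a flagged adolescent's age only to 18, which 6.3 counts as adult, so the rule does not do what it says it is for. The 11.5.2 example misstates the starting age (19 instead of 18) and then makes the subject older (18.004 against 18.001).

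The effect is confined to the maternal age and adolescent/adult demographic summaries. The number affected is not given and may be zero; one subject would be about 1% of the 97 enrolled (1/97 = 1.0%). Tabulation as an adult depends on the category being derived from numeric age, which the wording of the example suggests but no passage states. If the category comes from the flag, the defect is a reported age that contradicts it. The arithmetic is certain; the effect on the tables depends on that programming choice.

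**What to change.** In SAP 11.5.2 and 6.3:

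- State that the adolescent/adult category is taken from the CRF flag.
- Apply the adjustment when the flag is adolescent and the imputed age is 18 or more, not only above 18.
- Assign the earliest birth date in the recorded year that leaves her under 18 in completed years, that is, the day after the date exactly 18 years before the reference date. For a girl truly under 18 whose imputed age is 18, this always lies within her recorded birth year.
- Correct the example: the imputed age is 18 rather than 19, and the replacement birth date is 01Jul1998 (17.999 years, 17 completed years).
- In 6.3, set the adjusted age to 17 completed years instead of 18.
- Name one reference date, first treatment or randomization, in both sections.

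The cost is one derivation line and a few sentences. No data collection or model changes.
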